7.2.4 Brief Pain Inventory (BPI)

The BPI will consist of two domains, pain severity and pain interference with functioning.

Pain severity will be evaluated by rating pain on a scale from 0 (no pain) to 10 (pain as bad as you can imagine) for the 'worst', 'least', and 'average' pain experienced in the past 24 hours, as well as, the pain experienced 'now'. In addition, a calculated mean pain severity score will be based on the sum of all 4 of the pain scores divided by 4. If any of the 4 questions are missing, then the calculated mean pain severity score will be considered missing.

Pain interference with daily functioning will be evaluated by rating interference on a scale from 0 (does not interfere) to 10 (completely interferes) for 'general activity', 'mood', 'walking ability', 'normal work', 'relation with other people', 'sleep', and 'enjoyment of life'. A calculated mean pain interference will be based on the sum of non-missing interference questions answered divided by the number of questions answered. The mean should be set to missing if fewer than 4 pain interference questions are answered.

During the double-blind treatment period, the BPI will be collected on Days 84, 98, 112, and 119.

7.2.5 Patient Global Impression of Change (PGIC)

The PGIC rating represents observed changes (if any) from the subject's Baseline Visit in activity limitations, symptoms, emotions, and overall quality of life, related to the subject's painful condition. Change is rated on a 7-point Likert-type scale from 1 (no change) through 7 (a great deal better). During the double-blind treatment period, the PGIC will be collected on Days 84, 98, 112, and 119.

7.3 Pharmacokinetic Outcomes

Blood samples for determination of the steady state plasma pharmacokinetics (PK) of hydromorphone following continuous infusion will be collected during the study.

The total volume of blood drawn for PK analysis is 24 mL as four samples over the course of the study. Each PK sample will be a 6 mL of blood collected into a standard plasma sample tube and centrifuged to obtain at least 3 mL of plasma. The sample will be separated into two approximately 1.5 mL aliquots and frozen to $< -20^{\circ}$ C until shipment to the central testing facility.

Blood will be collected for analysis of hydromorphone concentration in plasma prior to dosing with any daily oral medications (i.e. other oral opioids permitted in the protocol) on Day 14, Day 56, 77 and Day 84.

8 Statistical Methods

8.1 Sample Size

Approximately 150 subjects will be enrolled at up to thirty (30) US investigative sites to obtain approximately 80 subjects who qualify for randomization into the double-blind period on Day 84. This enrollment is based on a combined drop out and treatment failure (i.e. > 50 mm on a 0 to 100 mm VASPI score for the last 5 days with non-missing data prior to the double-blind period) rate of approximately 45%.

During the double-blind period, the true treatment failure rate in the hydromorphone hydrochloride arm is assumed to be at most 20%. Based on a two-sided, two-sample comparison of proportions at the alpha=0.05 level of significance, a sample size of 80 subjects (40 per arm) will provide greater than 90% power to detect an increase in the treatment failure rate of 35% (i.e., the control group who will have their dose titrated downward has a failure rate of 55%).

8.2 Randomization and Masking

Each subject who is entered into the trial will be assigned an enrollment number by the site, that consists of the two digit site number (##) and a subject number consisting of three-digits (XXX) by the interactive web based randomization system. This number will be used for the entire duration of the trial.

For subjects who meet the criteria for randomization, a treatment group randomization code will be assigned to that subject via an interactive web-based randomization system (IWRS). The subject will then be randomized to either remain on the current dose of intrathecal hydromorphone or be titrated off therapy starting on Day 84 with a 1:1 ratio. The unblinded pump technician at the site will have access to the patient treatment assignment through accessing a separate page of the EDC on line. The unblinded pump technician will have a unique user name and password to allow them to access the treatment assignment.

This is a double-blind, randomized study. After randomization on Day 84, subjects will receive either intrathecal hydromorphone hydrochloride or will have their dose titrated downward over a 4 week period followed by 1 week at the lowest pump setting. An unblinded technician or nurse at the site will be assigned (i.e. Pump Operator) to adjust pump speeds during the 5 week double- blind period. The unblinded pump operator will not be involved in any other evaluations of the subject and will be instructed to avoid revealing any information to study personnel about the group assignment of the subject. Dosing after randomization will be done by randomization code for each subject. Subjects who utilize a PTM device will be blinded to the display screen of the PTM. The display screen will be covered with a non-transparent tamper resistant tape that will be checked at each visit. The PTM device will be able to operate normally, but the screen or any data from the PTM will not be visible to the subject.

8.3 Subject Discontinuation and Replacement of Subjects

Subjects may withdraw from the study at any time. Subjects may be discontinued from study treatment or the study at the request of the Investigator or Sponsor. Subjects who drop out of the study after randomization will not be replaced.

8.4 Final Analyses and Reporting

In addition, no database may be locked, randomization code unblinded, or final analyses completed until this SAP has been approved. The final analyses outlined in the protocol and in this SAP will be carried out after:

- The SAP has been approved;
- The study database has been authorized by the sponsor clinical team as complete and final;
- All analysis populations are determined; and
- Protocol violations have been identified.

Further exploratory analyses not necessarily identified in this SAP may be performed to support the clinical development program. Any post-hoc or unplanned analyses performed and not identified in this SAP will be clearly identified in the CSR.

8.5 Handling of Missing Data

Unless otherwise noted, missing data will not be imputed.

A subject who does not provide data sufficient to evaluate his/her treatment failure status during the double-blind period will **not** be considered to be a treatment failure. This includes subjects who drop out of the study during this period for any reason other than treatment failure. This methodology is aligned with the National Research Council (2010, page 24) report on missing data, the estimand is the difference in outcome improvement in tolerators. Because the primary endpoint is defined as a failure rate, and because any subject who cannot be defined as a "failure" is a treatment "success", the use of this endpoint in a randomized withdrawal study minimizes missing data (National Research Council, 2010, pages 33-34).

For all secondary efficacy endpoints (other than the time to rescue after randomization and oral opioid supplement consumption), last observation carried forward imputation (LOCF) will be used for missing data when performing an analysis at Day 119 or the last study visit.

Partially Answered Questionnaires:

When calculating the total score for the SF-MPQ, the Clinical Opiate Withdrawal Scale (COWS), and the Subjective Opiate Withdrawal Scale (SOWS), the 20% imputation rule will be used for partially answered questionnaires. If more than 20% of the items for the total

score are missing, then the total score will be set to missing. If 20% or less of the items for the total score are missing, then the total score will be calculated as:

(total of items present) \div (maximum possible total of items present) \times (maximum possible total of all items).

For the BPI, follow the rules for missing information discussed in the BPI section. Since the PGIC is a single question questionnaire, no imputation will be used.

8.6 Comments on Statistical Analysis

The following general comments apply to all statistical analyses and data presentations:

Summaries will include frequency and percentages for categorical data and frequency, mean, standard deviation, median, minimum, and maximum for quantitative data.

- Where appropriate and unless otherwise specified, analyses will be presented by randomized treatment arm: hydromorphone arm or titrated down (control) arm.
- Duration variables will be calculated using the general formula: Duration = (end date start date) + 1.
- Individual subject listings of all data represented on the eCRFs will be provided to facilitate the investigation of tabulated values and to allow for the clinical review of all data.
- Version 9.1 or greater of SAS statistical software package will be used to provide all summaries, listings, and graphs described in this document.
- All raw data will be presented to the original number of data places. The means and medians will be presented to one more decimal place than the raw data. The standard deviations will be presented to two more decimal places than the raw data. For averages of averages, the means and medians will also be presented to one more decimal place than the raw data and the standard deviations will also be presented to two more decimal places than the raw data.
- Generally, the denominator for percentages will be based on the number of subjects in the study population. However, for cases where appropriate, the denominator for percentages will be based on the number of subjects with non-missing data appropriate for summary purposes. Unless otherwise noted, all percentages will be presented to one decimal place.
- There are approximately 10-30 study sites in this study. Due to the large number of study sites and the small numbers of subjects per site, the analysis of efficacy endpoints will not include adjustments for study site. However, descriptive summaries of the primary endpoint will be provided by site.

• Analyses for the randomization phase, Day 84 through Day 119, will be calculated for the period defined as randomization date through end of study date, as study day of randomization and Day 119 visit may not always occur on the scheduled study days (84 and 119) due to various circumstances.

9 Statistical Analyses

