Prior to rescue medication being administered, subjects will complete Day 119 study assessments, if possible. After confirming with the investigator that it is acceptable to take rescue medication, if a subject cannot return to the study site for assessments they will be instructed to complete a VASPI score on the remote monitoring device immediately prior to taking oral rescue medication. If the subject can return to the site, rescue may be performed by either oral or IV medication being administered or by increasing the pump speed to achieve a therapeutic dose of hydromorphone hydrochloride, or both.

Subjects who are treatment failures or those who are dropped from the study prior to randomization under this protocol will be permitted to enroll into Mallinckrodt clinical study CNS-HYD202US if the PI believes that the subject meets the study selection criteria and would benefit from participation in the study. For any subject continuing therapy on the CNS-HYD202US trial, the Day 119 (or failure visit) assessments will be considered the last day on the CNS-HYD201US trial and the first day of CNS-HYD202US. Subjects in the CNS-HYD201US trial who were dropped prior to randomization and judged by the primary physician to benefit from participation in CNS-HYD202US will complete the study visit that they are on, go directly into CNS-HYD202US and complete scales there at the Screening and Baseline Visit. Subsequent visits, including re-titration onto hydromorphone hydrochloride if necessary, will be considered part of the CNS-HYD202 US trial.

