#### 9.7 Final Visit

Subjects who do not enter the CNS-HYD202US long-term safety trial will return to the investigational site for the final visit 2 weeks ( $\pm$  4 days) after discontinuation from the trial. At the final study visit subjects will be assessed for AEs and clinical signs or symptoms of an inflammatory granuloma as well as other procedures according to Appendix A, Table A- 2. Also during the final visit the investigator will remove all study drug from the subjects pump and will continue the subjects normal standard of care.

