#### 11.0 PREMATURE DISCONTINUATION FROM STUDY DRUG

The Investigator will continue to monitor subjects who have discontinued prematurely from study drug due to an AE (serious and non-serious) until resolution or stabilization of the AE.

The Investigator must complete all applicable electronic CRF pages for subjects who discontinue study drug prematurely. Final visit procedures (See Appendix A, Table A- 2) should be conducted for any subject who discontinues study drug prematurely.

01 August 2016 51 CONFIDENTIAL

If a subject is discontinued from therapy, study medication should be removed from the pump and the subject placed on standard of care therapy at the discretion of the investigator.

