7.1 Primary Efficacy Endpoint

The primary efficacy endpoint is the proportion of subjects who are treatment failures during the double-blind randomized withdrawal period. After randomization, a treatment failure will be defined by the following criteria:

- 1. Any subject who experiences an increase of 20 mm or more above the baseline value on a 100 mm VASPI based on the average of 5 days, or
- 2. Any subject who experiences intolerable pain that in the opinion of the investigator requires intervention (i.e. rescue), or
- 3. Any subject who has other interventions for pain that violate the protocol from Day 84 to 119 that includes:
 - a. Requires oral opioid supplement in excess of 60 mg/day morphine-equivalent to manage withdrawal symptoms, or
 - b. Has a change in non-opioid oral prescription medications or nonpharmacological treatments being administered for the management of pain.

Note: A subject who does not have sufficient data for evaluation, drops out for any other reasons that are not listed above or who experiences withdrawal syndrome as identified by COWS > 12 during the double-blind treatment phase will **not** be classified as a treatment failure in the primary efficacy analysis.

VASPI Calculation Algorithm

VASPI scores will routinely be collected twice each day. The daily VASPI score from Day 77 to 119 will be computed as follows:

- As the average of the two scores when both of the twice-daily VASPI measures are present.
- If only one score is present, then the daily score will be equal to that non-missing value.

• If both scores are missing, then the daily score will be missing.

The 5-day baseline (Days 77-83) average VASPI will be computed as follows:

- If the daily score is present on days 79, 80, 81, 82, and 83, then the 5-day average is the average of days 79-83.
- If one of the daily scores from days 79-83 is missing, then the day 78 value (if present) will be included in the 5 daily scores to be averaged. If the day 78 value is also missing, then the day 77 value will instead be used.
- If two of the daily scores from days 79-83 are missing, then the day 78 and day 77 values (if present) will be included in the 5 daily scores to be averaged.

During the double-blind randomized withdrawal period, the 5-day average will be calculated as follows:

- If the daily score is present on all 5 consecutive days, then the 5-day average will be calculated using the data from these days.

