9.5.1 Primary Efficacy Analysis

The primary efficacy endpoint is the proportion of subjects who are treatment failures during the double-blind randomized withdrawal period. After randomization, a treatment failure will be defined by the following criteria:

1. Any subject who experiences an increase of 20 mm or more above the baseline value on a 100 mm VASPI based on the average of 5 days, or

- 2. Any subject who experiences intolerable pain that in the opinion of the investigator requires intervention (i.e. rescue), or
- 3. Any subject who has other interventions for pain that violate the protocol from Day 84 to 119 that includes:
 - a. Requires oral opioid supplement in excess of 60 mg/day morphine-equivalent to manage withdrawal symptoms, or
 - b. Has a change in non-opioid oral prescription medications or nonpharmacological treatments being administered for the management of pain.

Note: A subject who does not have sufficient data for evaluation, drops out for any other reasons that are not listed above or who experiences withdrawal syndrome as identified by COWS > 12 during the double-blind treatment phase will **not** be classified as a treatment failure in the primary efficacy analysis.

The number and percentage of subjects with treatment failure during the double-blind period will be summarized by treatment group. Differences in treatment group failure rates will be test using a Pearson's chi-square (two-sided) test at the 5% level of significance. The corresponding 95% confidence interval for failure rate will be provided.

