	• Clarified calculations of opioid consumption.
	• Clarified the randomization period as the time from date of randomization
	through end of study, rather than Day 84 through Day 119.

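### SAP 8.6 ends the randomized phase at an undefined end of study date, so the oral opioid total, and conceivably the primary endpoint, can be counted over different lengths of time depending on roll-over

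*SAP*

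**What the plan says.** SAP 8.6, among comments that apply to all analyses, states that results for the randomized phase "will be calculated for the period defined as randomization date through end of study date". It gives one reason: "as study day of randomization and Day 119 visit may not always occur on the scheduled study days (84 and 119", the bracket holding the nominal days. The amendment summary in SAP Section 10 lists the change under 5.0 as running "through end of study, rather than Day 84 through Day 119". Neither the SAP nor the protocol, as supplied, defines end of study date.

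The end of a subject's participation depends on roll-over. For those continuing, Protocol 3.1 says "the Day 119 (or failure visit) assessments will be considered the last day on the CNS-HYD201US trial and the first day of CNS-HYD202US". For the others, Protocol 9.7 says "Subjects who do not enter the CNS-HYD202US long-term safety trial will return to the investigational site for the final visit 2 weeks". That interval is counted from when the subject leaves the trial, with a tolerance of 4 days either way. SAP Table 2, footnote f, counts the same 2 weeks from the last visit.

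The endpoint sections use three different end points:
- SAP 7.1 and 9.5.1 count failures in the double-blind period and limit criterion 3 to "other interventions for pain that violate the protocol from Day 84 to 119".
- SAP 7.2.3 totals oral opioid milligrams from Day 84 to the end of study. It adds concomitant-medication opioid records that start on or after randomization.
- SAP 9.5.2 analyses opioid consumption as a change to Day 119, and censors time to rescue at the date of last follow-up, which is also undefined.

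**The concern.** The comparison is designed for the five double-blind weeks. If the analysis window closes at Day 119 for subjects who roll over and at a later visit for those who do not, its length depends on a decision made after randomization, which may itself reflect how the subject fared. Cumulative quantities then differ for reasons unrelated to treatment. Pain treatment given after double-blind dosing could also enter a randomized-phase result.

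The timing adds weight. SAP Section 2 says the study was already unblinded when the sponsor decided to proceed with the efficacy analysis. An end date with two readings should be settled in the text, not during programming.

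**Working it through.** **Step 1: window length.** Inputs: Days 84 and 119 (SAP 8.6); Final Visit at 14 ± 4 days (Protocol 9.7, SAP Table 2).

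| Subject | End = actual Day 119 or failure visit | End = Final Visit |
|---|---|---|
| Completer, rolls over | 119 − 84 = 35 days | not applicable; the trial ends at Day 119 |
| Completer, does not roll over | 35 days | 35 + 14 = 49 days (35 + 10 = 45 to 35 + 18 = 53) |
| Failure before Day 119, does not roll over | days to failure visit | the same plus 10 to 18 days |

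The extension is 14/35 = 40%. The drift that 8.6 sets out to handle is far smaller: visits after Day 77 have a ±1 day window (Protocol Table A-2, footnote b).

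**Step 2: oral opioid total (SAP 7.2.3).** Concomitant medications are recorded until the final visit (SAP 9.2.2, Medications), so opioid taken after Day 119 is in the data. The rule for adding those records has a start date and no stop date. As an illustration, assume constant intake at the 60 mg/day morphine-equivalent limit:
- 35 days: 60 × 35 = 2,100 mg
- 49 days: 60 × 49 = 2,940 mg (45 to 53 days: 2,700 to 3,180 mg)

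The daily intake is the same and the total is 40% larger (29% to 51%). No adjustment for duration is planned. SAP 9.5.2 sets the analysis at Day 119, so the two sections do not agree on the end.

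**Step 3: primary endpoint, criterion by criterion.**
- Criterion 1 (VASPI rise): the device collects scores from Day 77 to 119 (SAP Section 5). Not materially exposed.
- Criterion 2 (rescue for intolerable pain): no day limit of its own, only the double-blind period in the endpoint sentence. Exposed if 8.6 redefines that period.
- Criterion 3 (other interventions): has its own Day 84 to 119 limit. Exposed only if 8.6 is taken to reinterpret those days.
- Drop-outs for other reasons: the Note in 7.1 and 9.5.1, and SAP 8.5, make them non-failures. Protected.

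That leaves completers who do not roll over.

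**Step 4: size, if that route were open.** The plan's power first, with n = 40 per arm, 20% vs 55%, two-sided 0.05 (SAP 8.1):
- pooled SE = √(2 × 0.375 × 0.625/40) = 0.1083
- unpooled SE = √(0.2 × 0.8/40 + 0.55 × 0.45/40) = 0.1009
- power = Φ[(0.35 − 1.96 × 0.1083)/0.1009] = 91.4%, which agrees with the stated figure of over 90%.

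The documents give no rate of treatment change after Day 119. Assume a share s of non-failures is reclassified, so p becomes p + (1 − p)s.

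Both arms affected equally:

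| s | Rates | Power |
|---|---|---|
| 5% | 24.0% vs 57.3% | 87% |
| 10% | 28.0% vs 59.5% | 82% |
| 20% | 36.0% vs 64.0% | 72% |

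Control arm only, with the true failure rate equal in both arms (exact enumeration of the chi-square test), chance of a significant result favouring the drug:

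| s | True rate 20% | True rate 30% |
|---|---|---|
| 0 | 2.6% | 2.4% |
| 5% | 6.3% | 5.0% |
| 10% | 13.0% | 9.4% |

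One subject is 1/40 = 2.5 points. Near the significance boundary two subjects matter: 8/40 vs 15/40 gives p = 0.084 and 8/40 vs 17/40 gives p = 0.030. At the planned rates, 8/40 vs 22/40 already gives p ≈ 0.001, and further control failures do not change the conclusion.

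**The case against.** The best defence is that 8.6 only replaces nominal days with actual dates. Its sentence pairs the randomization date with Day 84 and the end of study date with Day 119. Protocol 3.8 adds 2 + 5 + 12 + 5 weeks to 24, which leaves no room for a further two weeks. Protocol 9.7 places the Final Visit after discontinuation from the trial. The term may also be a case report form field, and those forms are not available here. This stands to the extent that the actual Day 119 visit is probably what was meant. It does not remove the ambiguity, because the SAP did not write that date and the protocol also calls the later visit the final study visit.

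A reader might go further and infer that end of study date is the Final Visit, so that ordinary post-study care counts as failure and inflates the control rate in the drug's favour. The documents do not support this. No section equates the two dates. Criterion 3 keeps its own days, and drop-outs for other reasons are declared non-failures. The instruction that "study medication should be removed from the pump and the subject placed on standard of care therapy at the discretion of the investigator" (Protocol 11.0) concerns premature discontinuation; for completers who do not roll over, Protocol 9.7 puts drug removal at the Final Visit itself. Controls do finish at about 0% dose, which makes later analgesia in that arm plausible, but nothing shows that only controls would be affected. If both arms were, the effect would be diluted.

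Nor are all randomized-phase analyses affected. The BPI and SF-MPQ models are set at Day 119, PGIC at Day 119 or rescue, and none of these scales is scheduled at the Final Visit.

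**Conclusion.** The point holds as an undefined analysis window that can give unequal follow-up. It is firmest for the 7.2.3 opioid total: under the Final Visit reading, a completer who does not roll over contributes 45 to 53 days against 35, with no correction. Censoring of time to rescue has the same kind of gap.

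For the primary endpoint the exposure is conditional. It needs completers who do not roll over, treatment meeting criterion 2 or 3 after Day 119, and a reading in which 8.6 overrides 7.1 and 9.5.1. The number of such subjects and the direction of any bias are unknown. The power and false-positive figures above show sensitivity under assumed shares and do not predict a bias. If the actual Day 119 visit was always intended, the definition changes no result. The point is worth fixing and ranks below must-fix.

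**What to change.** In SAP 8.6, define the end of the randomized phase as the earliest of the actual Day 119 visit date, the failure visit date and the date of discontinuation from double-blind dosing. Apply that cut-off to:
- the failure criteria in 7.1 and 9.5.1, so that treatment started later does not count toward criteria 2 or 3;
- the opioid total in 7.2.3, including records taken from the concomitant-medication form, and made consistent with the Day 119 analysis in 9.5.2;
- the censoring date for time to rescue in 9.5.2.

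Report anything later, including the Final Visit interval, separately as follow-up. Because the study is already unblinded, also show the results under the Final Visit reading as a sensitivity analysis, so that the choice of window is open to inspection.

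The cost is a few sentences in the SAP, a date cut-off in the programs and the sensitivity run. It uses dates already collected and leaves the locked data unchanged.
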